Alternative and more rapid approaches as an early indicator of negative sero-conversion in treated patients have been suggested. Using non-conventional serological techniques, i.e., highly sensitive and specific chemiluminescent ELISA using a purified trypomastigote glycoconjugate antigen and an epimastigote complex [20], the time to negativization was significantly sooner for the non-conventional ELISA than for the conventional ELISA. The chemiluminescent ELISAs provide tests that are highly sensitive and specific for Chagas' disease diagnosis. They can be used in blood bank screening and to monitor the treatment of patients undergoing chemotherapy [21].⁷⁶

Non-conventional ELISA antigens, such as those used in the Sosa-Estani and deAndrade trials (i.e., F29 and F 2/3), [15][16] are often considered as early markers for effective Chagas' disease therapy. In the study by Altcheh, et al, the kinetics of disappearance of conventional serology and anti-F2/3 antibodies were compared in 21 patients with congenital Chagas' disease after receiving benznidazole treatment. Patients were divided into two groups: (A) age < 8 months at diagnosis and (B) age > 9 months at diagnosis. Group A presented negative outcome for conventional serology at 6.6 months (CI 95 3.4-9.8 months) and for anti-F2/3 at 4 months (CI 95 0.9-7.1 months, p = 0.18). Group B exhibited nonreactive conventional serology at 63.1 months (CI 95 42.1-84.2 months) whereas anti-F2/3 antibody determination became negative at 21.9 months (CI 95 5.7-38.1 months, p = 0.0025). In patients belonging to Group A, antibodies were undetectable by both conventional serology and anti-F2/3 ELISA soon after receiving chemotherapy. In infants included in Group B, a negative result for anti-F2/3 antibody detection occurred significantly in advance of negative conventional serology reactivity. Consequently, the anti-F2/3 antibody assay becoming negative should be considered as a surrogate endpoint for assessment of cure or positive response to treatment, particularly in those patients with prolonged time of infection [18].

A new perspective on Chagas' disease diagnosis was opened by the use of the PCR as a measure of treatment response. Over the past few years, the availability of PCR to detect *T. cruzi* DNA in blood samples has opened new possibilities for the evaluation of response to trypanocidal chemotherapy.⁷⁷

Clearance of parasitemia (evaluated most commonly by xenodiagnoses or PCR) combined with disappearance of antibodies (seronegative conversion) has been proposed as cure criteria by some authors.[19] The main limitations in evaluating treatment response for Chagas' disease using conventional serology stems from the need for long-term follow-up (years to decades) to observe negativization of conventional serological tests.⁷⁸

⁷⁵ Term "titer(s)" replaced with "concentration(s)"; text modified for clarity (Amendment 1)

⁷⁶ Paragraph added to include updated information (Amendment 1)

⁷⁷ Paragraphs added to include updated information (Amendment 1)

⁷⁸ Text deleted from end of paragraph and moved to appear earlier in this section (Amendment 1)

	Integrated Clinical Study Protocol	
	BAY A2502 / 16027	
03 NOV 2020	Version 11.0	Page: 33 of 259

In the experience of Parasitology service, Ricardo Gutierrez Children's Hospital, Buenos Aires unpublished data (presented at European Society of Pediatric Infectious Disease 2014 and meeting of Food and Drug Administration) by PPD, a correlation between negativization of conventional serology (whole antibody against *T. cruzi* measured by ELISA or hemoagglutination inhibition) and PCR results in children 2 years of age and younger is fairly high; the correlation between these two tests in children older than 3 years is lower, as sero-conversion (i.e., becoming negative) may take several years, while PCR becomes negative within 60 days of treatment, and remains negative in this age group also. In the whole population, at least 20% sero-reduction of conventional serology was observed at 12 months. This percentage was higher in the younger children than in the older children.⁷⁹

By comparing 48 PCR methods from 26 laboratories, it was shown that the four best performing methods showed a high sensitivity (10 fg/ μ l DNA and 0.5 parasites/mL blood), and an overall accuracy of 87% to 90% [22]. More recent publications showed comparable sensitivity [23][24].

Several studies concluded that PCR has a higher sensitivity for detecting therapeutic failures compared to usual parasitological and conventional serologic methods. However, only two demonstrated specificity and showed that PCR could be used as a tool for early determination of cure [25][26].

Furthermore, real-time PCR (qPCR) protocols for detection of *T. cruzi*'s DNA were developed. The development of qPCR assays have several advantages compared with conventional PCR. First, the introduction of closed-tube qPCR systems has resulted in the development of rapid microbial diagnostics with low contamination risk. Also, qPCR has a shorter time-to-result, and allows quantitative assays and automation [27].⁸⁰

Studies have demonstrated the substantial value of qPCR, in terms of sensitivity and specificity, in the direct parasitological diagnosis of Chagas' disease and follow-up assessment of chemotherapy. However, in this Phase 3 study, parasitological cure based on serological tests for *T. cruz*i infection (ELISA) will be used as the primary efficacy endpoint to demonstrate efficacy of nifurtimox due to lack of historical PCR data from untreated children with Chagas' disease.⁸¹ Other parasitological methods (direct microscopic) and qPCR tests will comprise other variables to demonstrate drug efficacy.⁸²

The 30-day and 60-day treatment regimens were selected with the intention of providing the most effective treatment within the shortest possible duration. During the 1st Chagas Platform Technical meeting (September 1, 2009, Rio de Janeiro)[28] it was concluded that the minimum length of treatment for nifurtimox should be 30 days which is based on good results with fewer than 60 days of treatment. Hence, the 30-day arm is included to evaluate the potential of this shorter regimen.⁸³ In a recent study from Bianchi et al, 62 patients with Chagas' disease confirmed by different serological tests were treated with nifurtimox (Lampit), and followed for 30 months post-treatment. All children were treated during 60 days according to protocols established by the WHO. Monitoring was performed every 20

⁷⁹ Paragraph moved from previous page to here; text deleted (Amendment 1)

⁸⁰ Text modified for clarity (Amendment 1)

⁸¹ Text added for clarity (Amendment 1)

 $^{^{82}}$ Text deleted for clarity as of amendment 2

⁸³ Text added as per amendment 2

	Integrated Clinical Study Prote	ocol
	BAY A2502 / 16027	
03 NOV 2020	Version 11.0	Page: 34 of 259

days to evaluate treatment safety. Results indicated that both parasite load (measured through qPCR) and antibodies (ELISA absorbance) showed a significant median reduction 6 months after treatment from 6.2 to 0.2 parasite equivalents/mL, and from 0.6 to 0.2 absorbance units respectively (p<0.001). Further reductions were evidenced by the 30-month post-treatment time point. Sixty days of treatment with nifurtimox was very well tolerated and successfully reduced parasite load and antibody titers. The results show for the first time the therapeutic response and safety of nifurtimox treatment for *T. cruzi* infection in a population of schoolaged children in the asymptomatic chronic phase of Chagas' disease in Colombia [29].⁸⁴

End of part 1 of the study

The end of part 1 of the study as a whole will be reached as soon as the last visit of the last subject has been reached in all centers in all participating countries.⁸⁵

5.2 Part 2 (CHICO SECURE)

Design overview

This is a prospective, long-term follow-up of subjects, who were randomized and received at least one dose of their assigned 60- or 30-day nifurtimox treatment. The study is designed to evaluate seronegative conversion and serial reduction in OD measured by ELISA.

Subjects will be followed up for a total of 4 years after end of nifurtimox treatment. The first year of follow-up period is included in part 1 and 3 years of follow-up are included in part 2 of the study.

The following age categories will be considered for part 2 of the study: ≤ 2 years, ≥ 2 years to ≤ 6 years, ≥ 6 to ≤ 12 years, ≥ 12 to ≤ 18 years (age is defined as subject's age at randomization).

Subjects enrolled will be followed annually with visits to the investigational site. Seronegative conversion will be measured by two types of assay, recombinant ELISA, IHA, and by non-conventional ELISA.

For assessment of serial reduction compared to baseline defined as screening visit of part 1 (Visit 1), OD will be measured by recombinant ELISA and total purified antigen ELISA.

No study-specific procedures will be performed before the subject and/or parent(s) or legally authorized representative(s) has signed the informed consent form, or a minor subject has provided assent for part 2 of the study. After the consents/assents have been obtained, the assessments scheduled for FU Visit 1 including eligibility assessments will be performed. (FU Visit 1 according to Table 9–2; for details please refer to Section 9.2).

The first visit should be performed as soon as possible after availability of regulatory and ethics committee approval for all subjects who have already completed part 1 of the study for 1 year \pm 6 weeks or longer. Subjects who are entering the study beyond the time window for FU Visit 1 (2 years \pm 6 weeks) will have their eligibility assessments as soon as possible provided that consents/assents have been obtained (see Table 9–2; for details please refer to Section 9.2).

Subjects will have annual visits at the investigational site for efficacy and safety assessments for 3 years. Timing of study visits is relative to end of treatment in part 1 of the study.

⁸⁴ Text added for clarity (Amendment 1)

⁸⁵ Text modified as per amendment 2

	Integrated Clinical Study Protocol BAY A2502 / 16027	
03 NOV 2020	Version 11.0	Page: 35 of 259

At each investigational site visit, blood samples for serology tests (recombinant ELISA, total purified antigen ELISA, IHA, and non-conventional ELISA) will be collected. Blood samples will be taken under fasting conditions, if applicable, depending on the age of the subject, at the discretion of the investigator. Subjects will undergo a physical examination, body weight, height/length and vital signs will be measured and AEs considered at least possibly related to nifurtimox and AEs caused by protocol-required procedures will be recorded. A 12-lead electrocardiogram (ECG) will be obtained at each annual visit. The subject's concomitant medications will be recorded. Signs and symptoms of Chagas' disease will be assessed and blood will be taken for detection of *T. cruzi*'s deoxyribonucleic acid (DNA) using quantitative polymerase chain reaction (qPCR). If during the course of the study, OD measured by ELISA increases, the subject has positive qPCR results and shows signs or symptoms of Chagas' disease, it is up to the investigator's discretion to initiate antitrypanosomal treatment while the subject continues in the LTFU.

Whenever an AE considered at least possibly related to nifurtimox or caused by protocolrequired procedures occurs, the subject should report it to the investigator.

Female subjects who give birth before end of part 2 of the study will be invited to test their child for the presence or absence of infection with *T. cruzi*.

Between the annual visits at the investigational site, subjects and/or his or her parent(s) or legally authorized representative(s) will be contacted by qualified personnel by a method agreed (e.g., phone call) about 6 months after a visit at the investigational site to identify the occurrence of potential clinical symptoms of Chagas' disease or any pathology mentioned in the exclusion criteria using a structured interview. In case of suspected findings, an unscheduled visit at the investigational site to initiate appropriate diagnostic evaluations will be requested.

The schedule of procedures/assessments to be performed during part 2 of the study is provided in Section 9.1.

Primary variable

The primary efficacy variable will be the incidence rate of seronegative conversion measured by two types of assay (recombinant ELISA and IHA) in subjects who were randomized and received at least one dose of the 60-day nifurtimox treatment regimen. Both test results should be negative for the subject to be considered as seroconverted.

End of part 2 of the study

The end of part 2 of the study as a whole will be reached as soon as the last visit of the last subject has been reached in all centers in all participating countries.

Primary completion

The primary completion event for part 2 of the study is last subject last visit (LSLV).

Justification of the design

For the monitoring of efficacy of antitrypanosomal treatment, the criterion of cure usually depends on serologic conversion of the anti-*T. cruzi* antibody response to negative. Seronegative conversion in children and adolescents may occur several years after treatment, requiring long-term follow-up. Conversion of serological responses to negative, demonstrated by more than one type of assay (ELISA and either IHA or IFA) is the FDA-accepted clinical criterion of cure.

	Integrated Clinical Study Protocol	
	BAY A2502 / 16027	
03 NOV 2020	Version 11.0	Page: 36 of 259

Annual visits at the investigational site are planned for efficacy and safety measurements and subjects will be closely monitored for signs and symptoms of Chagas' disease. Criteria for withdrawal of individual subjects or termination of the entire study are described in Section 6.3 and Section 12, respectively.

It is well known, that mothers with Chagas' disease can transmit *T. cruzi* to their fetuses, who become carriers of the infection and are then at risk of developing severe cardiac disease later in the course of their lives. If identified early enough after birth, the infected newborns can be treated and cured.

6. Study population

6.1 Inclusion criteria

Inclusion criteria for part 1 (CHICO)

- 1. Male and female pediatric subjects aged 0 days to younger than 18 years
- 2. Chagas' disease diagnosed/confirmed by:
 - Subjects < 8 months of age at randomization must demonstrate direct observation of *T. cruzi* by concentration test⁸⁶
 - Subjects ≥ 8 months to < 18 years of age at randomization must demonstrate a positive conventional ELISA result for both of the following tests to confirm diagnosis:
 - Recombinant ELISA
 - Total purified antigen ELISA⁸⁷

Additionally, a non-conventional ELISA test and IHA ^{88,89} will be obtained; however, a positive result will not be required for diagnosis.

Subjects will also be eligible if there is acceptable documentation (two ELISA tests) of positive Chagas' disease within three months prior to screening and they have not had prior anti-trypanocidal or anti-parasitic treatment.⁹⁰ (The subject's parent or legally acceptable representative must agree to the collection of a baseline blood specimen for ELISA testing later during the study).⁹¹

- 3. Written informed consent by the subject and/or parent(s) or legally authorized representative(s) according to the age established per local regulations must be obtained from all subjects who are screened for the study. In addition, depending on the subject's age, subject's assent is required as applicable by local laws and regulations (varies in each country).
- 4. Females of childbearing potential (i.e., female subjects who have experienced menarche) and male subjects must agree to use adequate contraception if sexually active from the time of signing the informed consent/assent form until 3 months after the last study drug

⁸⁶ Text modified for clarity (Amendment 1)

⁸⁷ Text modified/added for clarity and per Modification 2 (Amendment 1)

⁸⁸ IFA test added per Amendment 5

 $^{^{89}}$ Replaced IFA with IHA per Amendment 6.

⁹⁰ Text added per Modification 2 (Amendment 1)

⁹¹ Text added as per amendment 2.

	Integrated Clinical Study Protocol	
	BAY A2502 / 16027	
03 NOV 2020	Version 11.0	Page: 37 of 259

administration. Depending on the country, study site personnel may dispense condoms at the time that study drug is dispensed to either the subject or the subject's parent/legal guardian, with an explanation of rationale and risks.

Inclusion criteria for part 2 (CHICO SECURE)

- 1. Male and female subjects who were randomized and received at least one dose of their assigned 60- or 30-day regimen of nifurtimox treatment
- 2. Written informed consent by the subject and/or parent(s) or legally authorized representative(s) according to the age established per local regulations must be obtained from all subjects who are screened for the study. In addition, depending on the subject's age, subject's assent is required as applicable by local laws and regulations (varies in each country)

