03 NOV 2020

Version 11.0

Page: 27 of 259

[figure not shown]

Figure 5–1: Study Design of Part 1 – Protocol 16027⁴⁵

site for study assessments at Visits 3, 6, and 8 (EOT), and undergo telephone assessments as described for Visits 4, 5, and 7. If subjects are unable/unwilling to do so, they must return to the investigational site 30 (±3) days after the last dose of study drug for EOT (Visit 8) assessments, and undergo telephone assessments as described for Visits 4, 5, and 7. If the subject is unable/unwilling to return to the clinic for the EOT Visit (Visit 8), then a telephone assessment as described for Visits 4, 5, and 7 may be performed in lieu of Visit 8 assessments.

This study will enroll pediatric subjects aged 0 to younger than 18 years. Subjects < 8 months of age at randomization with a diagnosis of Chagas' disease must demonstrate direct observation of *T. cruzi* by concentration test, and subjects \ge 8 months to < 18 years of age at randomization with a diagnosis of Chagas' disease must demonstrate a positive conventional ELISA result for both of the following tests to confirm diagnosis:⁴⁶

- Recombinant ELISA
- Total purified antigen ELISA

Additionally, a non-conventional ELISA test and IHA ^{47,48} will be obtained; however, a positive result will not be required for diagnosis.

Subjects will also be eligible if there is acceptable documentation of positive Chagas' disease within three months prior to screening.⁴⁹

⁴⁵ Figure modified as a result of changes made to the protocol per Amendment 1; Visit 4 changed to 14 ± 1 day; Visit 5 was made a telephone assessment at 21 ± 3 days; visits renumbered from that point forward; footnote b deleted; footnote c re-lettered to footnote b; text to new footnote b changed per Modification 11 (Amendment 1)

⁴⁶ Text modified for clarity (Amendment 1)

⁴⁷ IFA test added per Amendment 5.

⁴⁸ Replaced IFA with IHA per Amendment 6.

⁴⁹ Text modified/added per Modification 2 (Amendment 1)

	Integrated Clinical Study Pro	tocol
	BAY A2502 / 16027	
03 NOV 2020	Version 11.0	Page: 28 of 259

Approximately 300 pediatric subjects will be randomized (2:1 randomization, 60-day regimen vs. 30-day regimen).⁵⁰ Subjects will be stratified by age at randomization into four strata as specified below:⁵¹

Stratum 1:52	0 to 27 days
Stratum 2:	28 days to younger than 8 months
Stratum 3:	8 months to younger than 2 years
Stratum 4:	2 years to younger than 18 years

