9.2 Visit description

9.2.1 Screening

9.2.1.1 Visit 1 – screening visit (Days -14 to -1)

No study-specific procedures will be performed before the subject/legally authorized representative signs the informed consent form, or a minor subject provides assent, including asking a potential subject to fast (if applicable, depending on the age of the subject at the discretion of the investigator) prior to the screening blood samples. Informed consent/assent for optional PK blood sampling will also be obtained. After the consents/assents have been obtained, the following assessments will be performed:

- Collection of demographic data
- Medical and surgical history, including date of menarche for female subjects, and method of contraception
- Evaluation of inclusion and exclusion criteria
- Assessment of Chagas' disease signs and symptoms (to be performed during physical examinations); see Section 9.4.4
- Concentration test for *T. cruzi* (subjects <8 months of age at randomization) and conventional serologic testing for Chagas' disease (subjects ≥ 8 months < 18 years of age) conducted in local laboratory (or acceptable documentation of positive Chagas' disease within 3 months prior to screening and no prior anti-trypanocidal or anti-parasitic treatment). Specimens taken for conventional serology, non-conventional serology, IHA, and qPCR will be frozen and stored at -20°C prior to shipment to the central laboratory where they will be stored at -70°C.^{117,118}
- Assessment of pretreatment AEs and concomitant medications
- A complete physical examination of body systems. Abnormal findings will be documented as medical history (see Section 9.6.1.1).
- Neurological examination (see Section 9.6.3.3). Abnormal findings will be documented as medical history (see Section 9.6.1.1).
- Vital signs (blood pressure is optional in subjects < 5 years of age at the discretion of the investigator), height/length, and weight
- 12-lead ECG (optional in subjects < 5 years of age at the discretion of the investigator)
- Serum hematology and chemistry, coagulation, and urinalysis (if urine specimen can be obtained). Fasting is dependent on the age of the subject at the discretion of the investigator.

¹¹⁷ Modified as per Amendment 2 and Amendment 5.

¹¹⁸ Replaced IFA with IHA per Amendment 6.

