9.4.2 Serological tests

At screening, subjects must have the following serological tests to confirm a diagnosis of Chagas' disease:

- Subjects < 8 months of age at randomization must demonstrate direct observation of *T. cruzi* by concentration test¹⁴⁹
- Subjects ≥ 8 months to < 18 years of age at randomization must demonstrate a positive conventional ELISA result for both of the following tests to confirm diagnosis:
 - Recombinant ELISA
 - Total purified antigen ELISA¹⁵⁰

Additionally, a non-conventional ELISA test and IHA will be obtained; however, a positive result will not be required for diagnosis^{151,152}.

Subjects will also be eligible if there is acceptable documentation of positive Chagas' disease within 3 months prior to screening and they have had no prior anti-trypanocidal or anti-parasitic treatment.¹⁵³

After randomization, conventional and non-conventional serological tests will be performed at Visits 3, 6, and 8 (EOT), and Visits 10 and 11 (Follow-up).¹⁵⁴

All subjects ≥ 8 months to < 18 years of age at randomization will have two baseline specimens collected for serologic testing. One sample will be used to determine the initial diagnosis of Chagas' disease while the other sample will be frozen and retained to be assayed later as an internal control. Subjects < 8 months of age at randomization will have one specimen obtained, which will be frozen and retained. Total blood volume to be taken for the

¹⁴⁸ Modified as per amendment 2

¹⁴⁹ Text modified for clarity (Amendment 1)

¹⁵⁰ Text modified for clarity and per Modification 2 (Amendment 1)

¹⁵¹ IFA test added per Amendment 5.

¹⁵² Replaced IFA with IHA per Amendment 6.

¹⁵³ Text modified/added for clarity and per Modification 2 (Amendment 1)

¹⁵⁴ Text modified for clarity and to reflect changes per Amendment 1

	Integrated Clinical Study Protocol BAY A2502/ 16027
03 NOV 2020	Version 11.0

required three serological and PCR tests is 4.0-5.0 mL, depending on the subject's age. Care will be taken to minimize sample volumes by using a micro-sampling collection technique, when possible.¹⁵⁵

Page: 63 of 259

Details describing the collection, processing, storage and shipment of blood samples, and the serologic test protocols, will be described in a separate serologic test manual from the central laboratory.

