9.4.3 Concentration tests for *T. cruzi*

Concentration tests for *T. cruzi* will be performed on all subjects < 8 months of age at randomization at the screening visit, and at Visits 3, 6, 8 and 9.

Details describing the collection, processing, storage and shipment of blood samples, and the concentration test protocol, will be described in a separate manual. Concentration tests for *T. cruzi* will be performed by a local laboratory according to the standard of care for each country.¹⁵⁶

Concentration test for *T. cruzi* is not applicable for subjects in part 2 of the study. However, concentration test for *T. cruzi* may be performed in children born of female study subjects to detect congenital infection (see Section 9.6.2).

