9.6.2 Pregnancies

Part 1 (CHICO)

Any subject who becomes pregnant during the course of the study will discontinue study treatment. Pregnancy must be confirmed by serum pregnancy test. The investigator must report to the sponsor any pregnancy occurring in a female study subject during her participation in this study. The outcome of the pregnancy should be followed up carefully, and any outcome of the mother and the child at delivery should be reported.

For a pregnancy in the partner of a male study subject, all efforts will be made to obtain similar information on course and outcome, subject to the partner's consent and any abnormal outcome of the child should be reported.

For all reports, the forms provided are to be used. The investigator should submit them within the same timelines as an SAE.

Part 2 (CHICO SECURE)

At each visit in part 2, female subjects will be asked if she is pregnant or gave birth to a baby after the first dose of nifurtimox treatment regimen or since the last visit.

The investigator must report to the sponsor any pregnancy occurring in a female study subject during her participation in this study. The outcome of the pregnancy should be followed up carefully, and any outcome of the mother and the child at delivery should be reported.

Female subjects who give birth by the end of part 2 of the study will be invited to test their child for the absence or presence of infection with *T. cruzi*, except if the child was already tested according to the standards of the country or has already received treatment for Chagas' disease. The congenital infection will be confirmed by parasitological method in children ≤ 8 months of age and by serological method in children >8 months of age. Efforts should be made to obtain the results of congenital infection testing when already done according to the standards of the country. The result of congenital infection will be documented in the applicable eCRF form.

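### The documentation route in inclusion criterion 2 states no age limit and no age at sampling, which conflicts with the parasitological requirement under 8 months and could let antibody loss be scored as cure

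*Protocol*

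**What the plan says.** Protocol 6.1, criterion 2, sets the diagnostic test by age. For the youngest: "Subjects < 8 months of age at randomization must demonstrate direct observation of" T. cruzi by concentration test. From 8 months, both conventional ELISAs must be positive. A further sentence then opens an alternative: "Subjects will also be eligible if there is acceptable documentation (two ELISA tests") within three months before screening, with no prior treatment. It gives no age limit and no age at which the documented samples must have been drawn.

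The route recurs in the synopsis, 5.1 ("Subjects will also be eligible if there is acceptable documentation of positive" disease), 9.2.1.1 and 9.4.2 ("Subjects will also be eligible if there is acceptable documentation of positive Chagas' disease within 3 months prior to screening"). None of these four mentions ELISA, and none limits age. In 9.2.1.1 the clause "or acceptable documentation of positive Chagas' disease within 3 months prior to screening and no prior anti-trypanocidal or anti-parasitic treatment" comes after both the infant concentration test and the older child's serology.

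For babies born to participants, Protocol 4.2, 9.2.4 and 9.6.2 require parasitological confirmation up to 8 months and allow confirmation "by serological method in children >8 months of age".

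On scoring, two negative ELISAs at 12 months are a cure at any age (Protocol 10.3.1.1, SAP 6.2.1.1). In Part 2, negative recombinant ELISA and IHA together are a seronegative conversion (Protocol 10.3.1.2, SAP 6.2.2.1).

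**The concern.** An antibody result in a young infant need not mean that the infant is infected. The protocol seems to recognise this, since it relies on parasitology up to 8 months both for enrolment and for participants' babies. The documentation sentence, taken at face value, bypasses that safeguard.

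A child admitted on passively acquired antibody would be expected to lose it whatever the treatment, and the endpoint would record the loss as success. In the comparisons with historical controls this error could only raise the nifurtimox result. The controls were aged 7 to 12 and 6 to 12 years (Protocol 10.4), so the 16% goal makes no allowance for antibody loss in infancy. Uninfected infants could also be exposed to study drug.

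**Working it through.** **Can an infant enter on ELISA alone?**

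- Under 8 months: one sentence of 6.1 demands direct observation; another makes subjects eligible on two documented ELISAs. The second is worded as an additional route and carries no age condition.
- At 9.2.1.1, the bracketed alternative can attach to both preceding tests or only to the serology.
- At 9.4.3 the concentration test "will be performed on all subjects < 8 months of age at randomization at the screening visit", but no text says that it must be positive when documentation is used.
- Even if the route is meant only for children of 8 months or more, age is judged at randomisation, not at sampling. Documentation may precede screening by 3 months. Screening may precede randomisation by 14 days, extendable by 3 (6.3.1). That is 3 months + 17/30.4 months, about 3.5 months, so a child randomised at 8 to about 11.5 months could rely on samples drawn before 8 months.

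**Would the analysis remove such a child?**

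- The per-protocol set (SAP 5.1) drops children who fail the entry criteria; this child meets them as written.
- The Part 1 sensitivity analyses (SAP 6.2.1.1) concern missing data and the per-protocol set.
- Part 2 names only the full analysis set, and the SAP lists no sensitivity analysis for it.
- Visit 11 is Day 420 (420/30.4 = 13.8 months), so a child under 8 months at entry is then about 14 to 22 months old.

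**Part 1 arithmetic.** Inputs: n = 200 in the 60-day arm, planned cure rate 55%, goal 16%, stated power 99% (Protocol 10.4). The SAP lower limit is p − 1.96√(p(1−p)/n) − 1/(2n).

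- The smallest passing count is 44: 0.22 − 0.0574 − 0.0025 = 16.01%; 43 gives 15.6%. Power at 55% exceeds 99.9%, so the plan's figure is reproduced. Exact type I error at a true 16% is 1.6%.
- If strata 1 and 2 reach 38 each, about 2 × 38 × 2/3 = 51 of the 60-day arm are under 8 months. The targets are not mandatory.
- Let u be the number of uninfected infants scored as cured; u is assumed throughout. Against scoring them as not cured, the rate rises by u/200: 1.5, 2.5, 5.0 and 7.5 points for u = 3, 5, 10 and 15. Against excluding them, with 55% cured in the rest, the rise is 0.45u/200: 0.7 points for u = 3 and 3.4 for u = 15.
- At 55% with u = 0 the lower limit is 47.9%, far above 16%.
- Only if the true rate in the rest were 16% would the test itself suffer: type I error would be 8.0% at u = 5 and 44.5% at u = 13.

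**Part 2 arithmetic.** Planned events are 5% of 170 = 8.5 (Protocol 10.4, SAP 6.5). The same u, if all remain in follow-up, would add u/8.5:

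| u | Share of planned events |
|---|---|
| 3 | 35% |
| 5 | 59% |
| 10 | 118% |
| 15 | 176% |

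**The case against.** The strongest reply is that the narrow reading is the intended one. The two-ELISA wording mirrors the rule for children of 8 months or more. Section 9.4.2 assigns a diagnostic serology specimen only to that group; younger infants give one specimen, which is frozen. Section 9.4.3 schedules the concentration test for all younger infants with no exception for documentation, and 9.2.2.1 waits for screening results and rechecks eligibility. The four parallel passages, which never mention ELISA, fit documentation of whichever test the age requires. This stands as evidence of intent. It does not settle the conflict inside 6.1, and it leaves age at sampling open.

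It also stands that the documents never name maternal antibody or say when it clears, and that SAP 6.1.2 and 6.2.1.1 already tabulate baseline test results and Part 1 cure by age stratum, so inflation in the infant strata would be partly visible. The pooled primary result would still contain it.

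A reader might infer three stronger things that the documents do not support:

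- *That every planned comparison is biased towards nifurtimox.* In the randomised 60- versus 30-day comparison such infants are expected in both arms and would tend to dilute a difference.
- *That one such infant makes Part 2 succeed.* One event in about 680 person-years does give a lower limit of 0.0037%, but that fragility comes from the 0% comparator and is a separate matter.
- *That these children should leave the primary analyses.* Concentration tests are scheduled only under 8 months, so for children randomised at 8 to about 11.5 months exclusion would rest on Visit 1 qPCR alone. The protocol does not use qPCR for diagnosis, and cites 87% to 90% accuracy for the best PCR methods (5.1).

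**Conclusion.** The point holds as a conflict in the eligibility text with a consequence for scoring. It does not show that infants were meant to enter, or did enter, on serology alone.

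The size rests on three assumptions: that some infants used the route, that their antibody was passively acquired, and that it had gone by the assessment. Under them, 3 to 15 infants of 200 would raise the 60-day cure rate by up to 1.5 to 7.5 points. The Part 1 conclusion at the planned 55% would be unchanged; the harm is an inflated rate, concentrated in strata 1 and 2. Part 2 is more exposed, because the same number of children is 35% to 176% of its planned conversions.

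**What to change.** Reconcile Protocol 6.1, 5.1, 9.2.1.1, 9.4.2 and the synopsis so that documentation must be of the test required for the child's age, and state the age at which the documented sample must have been drawn.

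Add to the SAP one prespecified sensitivity analysis of the Part 1 and Part 2 primary endpoints. It should exclude, or score as not converted, children admitted on ELISAs drawn before 8 months without parasitological confirmation at entry. Confirmation means a positive concentration test where one was done; for children of 8 months or more at randomisation only the Visit 1 qPCR is available. Report how many children this concerns, and keep the full analysis set as primary.

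The cost is a clause in each eligibility passage, a short SAP paragraph and a little more analysis; no new sample is needed. The sensitivity estimate may be slightly lower and may drop some truly infected children with undetectable qPCR, which is why it should not replace the primary result.
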